#### 4.2 Cancer Trials Support Unit Registration Procedures

Permission to view and download this protocol and its supporting documents is restricted and is based on person and site roster assignment housed in the Roster Maintenance application and in most cases viewable and manageable via the Roster Update Management System (RUMS) on the Cancer Trials Support Unit (CTSU) members' website. This study is supported by the NCI CTSU.

##### IRB Approval

As of March 1, 2019, all U.S.-based sites must be members of the NCI Central Institutional Review Board (NCI CIRB) in order to participate in Cancer Therapy Evaluation Program (CTEP) and Division of Cancer Prevention (DCP) studies open to the National Clinical Trials Network (NCTN) and NCI Community Oncology Research Program (NCORP) Research Bases. In addition, U.S.-based sites must accept the NCI CIRB review to activate new studies at the site after March 1, 2019. Local IRB review will continue to be accepted for studies that are not reviewed by the CIRB, or if the study was previously open at the site under the local IRB. International sites should continue to submit Research Ethics Board (REB) approval to the CTSU Regulatory Office following country-specific regulations.

Sites participating with the NCI CIRB must submit the Study Specific Worksheet (SSW) for Local Context to the CIRB using IRBManager to indicate their intent to open the study locally. The NCI CIRB's approval of the SSW is automatically communicated to the CTSU Regulatory Office, but sites are required to contact the CTSU Regulatory Office at [[contact]](mailto:[contact]) to establish site preferences for applying NCI CIRB approvals across their Signatory Network. Site preferences can be set at the network or protocol level. Questions about establishing site preferences can be addressed to the CTSU Regulatory Office by email or calling [name].

Sites using their local IRB or REB, must submit their approval to the CTSU Regulatory Office using the Regulatory Submission Portal located in the Regulatory section of the CTSU website. Acceptable documentation of local IRB/REB approval includes:

- Local IRB documentation;
- IRB-signed CTSU IRB Certification Form; and/or
- Protocol of Human Subjects Assurance Identification/IRB Certification/Declaration of Exemption Form.

In addition, the Site-Protocol Principal Investigator (PI) (i.e. the investigator on the IRB/REB approval) must meet the following criteria for the site to be able to have an Approved status following processing of the IRB/REB approval record:

- Have an active CTEP status;
- Have an active status at the site(s) on the IRB/REB approval (*applies to US and Canadian sites only*) on at least one participating organization's roster;
- If using NCI CIRB, be active on the NCI CIRB roster under the applicable CIRB Signatory Institution(s) record;
- Includes the IRB number of the IRB providing approval in the Form FDA 1572 in the RCR profile;
- Lists all sites on the IRB/REB approval as Practice Sites in the Form FDA 1572 in the RCR profile; and
- Have the appropriate CTEP registration type for the protocol.

#### **Additional Site Registration Requirements**

Additional site requirements to obtain an approved site registration status include:

- An active Federal Wide Assurance (FWA) number;
- An active roster affiliation with the Lead Protocol Organization (LPO) or a Participating Organization (PO);
- An active roster affiliation with the NCI CIRB roster under at least one CIRB Signatory Institution (US sites only); and
- Compliance with all applicable protocol-specific requirements (PSRs).

#### **4.2.1 Downloading Site Registration Documents**

Download the site registration forms from the protocol-specific page located on the CTSU members' website. Permission to view and download this protocol and its supporting documents is restricted to institutions and their associated investigators and staff on a participating roster. To view/download site registration forms:

- Log in to the CTSU members' website (<https://www.ctsu.org>)
- Click on *Protocols* in the upper left of the screen
  - Enter the protocol number in the search field at the top of the protocol tree, or
  - Click on the By Lead Organization folder to expand, then select *Alliance* and protocol number *A021502*.
- Click on *Documents, Protocol Related Documents*, and use the *Document Type* filter and select *Site Registration* to download and complete the forms provided. (Note: For sites under the CIRB, IRB data will load automatically to the CTSU)

#### **4.2.2 Submitting Regulatory Documents**

Submit required forms and documents to the CTSU Regulatory Office using the Regulatory Submission Portal on the CTSU members' website.

To access the Regulatory Submission Portal log in to the CTSU members' website, go to the *Regulatory* section and select *Regulatory Submission*.

Institutions with patients waiting that are unable to use the Regulatory Submission Portal should alert the CTSU Regulatory Office immediately by phone or email: [name], or [[contact]](mailto:[contact]) to receive further instruction and support.

**NOTE: Until institutions receive a formal notice from the Alliance regarding termination to patient follow-up, institutions must not close this trial with the IRB of record for the study. Alliance members may refer to section 6.14 of the Alliance's Policy and Procedures for additional information about study termination, or institutions may contact the Alliance Regulatory team at [[contact]](mailto:[contact]) with any questions.**

#### 4.2.3 Checking Site Registration Status

Site registration status may be verified on the CTSU members' website.

- Click on *Regulatory* at the top of the screen;
- Click on *Site Registration*; and
- Enter the site's 5-character CTEP Institution Code and click on Go.
  - Additional filters are available to sort by Protocol, Registration Status, Protocol Status, and/or IRB Type.

Note: The status shown only reflects institutional compliance with site registration requirements as outlined within the protocol. It does not reflect compliance with protocol requirements for individuals participating on the protocol or the enrolling investigator's status with NCI or their affiliated networks.

#### 4.2.4 Delegation of Tasks Log (DTL)

Each site must complete a protocol-specific Delegation of Tasks Log (DTL) using the DTL application in the Delegation Log section on the CTSU members' website. The Clinical Investigator (CI) is required to review and electronically sign the DTL prior to the site receiving an approved site registration status and enrolling patients to the study. To maintain an approved site registration status the CI must re-sign the DTL at least annually and when a new version of the DTL is released; and activate new task assignments requiring CI sign-off. Any individual at the enrolling site on a participating roster may initiate the site DTL. Once the DTL is submitted for CI approval, only the designated DTL Administrators or the CI may update the DTL. Instructions on completing the DTL are available in the Help Topics button in the DTL application and describe DTL task assignments, CI signature, and CTEP registration requirements, as well as include a Master Task List.

### 4.3 Patient Registration Requirements

**Informed Consent:** For patients  $\geq 18$  years of age: the patient must be aware of the neoplastic nature of his/her disease and willingly consent after being informed of the procedure to be followed, the experimental nature of the therapy, alternatives, potential benefits, side-effects, risks, and discomforts. Current human protection committee approval of this protocol and a consent form is required prior to patient consent and registration. Patients with impaired decision

making capacity may be enrolled on this study, where institutional policy and IRB of record allow. For patients aged 12 to <18 years: patients and/or their parents or legal guardians must sign and give written informed consent and assent in accordance with institutional and federal guidelines.

**Protected Health Information:** Some of the tissue specimens collected for this study will be sent directly to a central laboratory agreed upon by the Alliance and the drug company supporting this study. These samples (or the required requisition form) will be labeled with study ID, surgical pathology number/block ID, and collection date. Some of the blood specimens collected for this study will be sent directly to Duke University. These samples will be labeled with patient initials, study ID, and collection date.

**Patient-completed Booklets:** Patient questionnaire booklets are to be ordered prior to the registration of any patients. Patient completed booklets can be ordered by downloading and completing the CTSU supply request form (located under the site registration documents section of the A021502 CTSU site) and submitting it through the CTSU regulatory portal. Samples of the booklets are found in [Appendix I](#), which are to be used for reference and IRB submission only. They are not to be used for patient completion. There is one booklet for PRO-CTCAE which is required per the study calendar for all patients. There is a second QOL booklet for patients who consent for the Quality of Life study. There is no booklet for the Registration Fatigue/Uniscale assessment (first page of [Appendix I](#), required for all patients per the study calendar). If needed, the first page of [Appendix I](#) can be adapted to use as a source document.

#### 4.4 Patient Registration/Randomization Procedures

The Oncology Patient Enrollment Network (OPEN) is a web-based registration system available on a 24/7 basis. OPEN is integrated with CTSU regulatory and roster data and with the LPOs registration/randomization systems or the Theradex Interactive Web Response System (IWRS) for retrieval of patient registration/randomization assignment. OPEN will populate the patient enrollment data in NCI's clinical data management system, Medidata Rave.

Requirements for OPEN access:

- Active CTEP registration with the credentials necessary to access secure NCI/CTSU IT systems;
- To perform enrollments or request slot reservations: Must be on an LPO roster, ETCTN corresponding roster, or participating organization roster with the role of Registrar. Registrars must hold a minimum of an Associate Plus (AP) registration type;
- If a Delegation of Tasks Log (DTL) is required for the study, the registrars must hold the OPEN Registrar task on the DTL for the site; and
- Have an approved site registration for the protocol prior to patient enrollment.

To assign an Investigator (IVR) or Non-Physician Investigator (NPVR) as the treating, crediting, consenting, drug shipment (IVR only), or receiving investigator for a patient transfer in OPEN, the IVR or NPVR must list the IRB number used on the site's IRB approval on their Form FDA 1572 in RCR. If a DTL is required for the study, the IVR or NPVR must be assigned the appropriate OPEN-related tasks on the DTL.

Prior to accessing OPEN, site staff should verify the following:

- Patient has met all eligibility criteria within the protocol stated timeframes; and
- All patients have signed an appropriate consent form and Health Insurance Portability and Accountability Act (HIPAA) authorization form (if applicable).

Note: The OPEN system will provide the site with a printable confirmation of registration and treatment information. You may print this confirmation for your records.

Access OPEN at <https://open.ctsu.org> or from the OPEN link on the CTSU members' website. Further instructional information is in the OPEN section of the CTSU website at <https://www.ctsu.org> or <https://open.ctsu.org>. For any additional questions, contact the CTSU Help Desk at [name] or [[contact]](mailto:[contact]).

### **COG Patient Registration Enrollment Information**

For COG Credited Enrollments ONLY: Prior to enrollment on this study, patients enrolling must be assigned a COG patient ID number. This number is obtained via the Patient Registry module in OPEN once authorization for the release of protected health information (PHI) has been obtained. The COG patient ID number is used to identify the patient in all future interactions with COG. If you have problems with the registration, please refer to the online help. For additional help or information, please contact the CTSU Help Desk at [name] or [[contact]](mailto:[contact]).

Note: This COG patient ID number is different from the A021502 patient ID which will be assigned during registration (Step 1) to this trial.

## **4.5 Registration to Correlative Studies**

There are three substudies within Alliance A021502. These correlative science studies must be offered to all patients  $\geq 18$  years of age enrolled on Alliance A021502 (although patients may opt to not participate); patients 12 to  $< 18$  years of age may not participate in the Quality of Life Study (A021502-HO1), but must be offered the other two substudies. These substudies do not require separate IRB approval. The substudies included within Alliance A021502 are:

- Quality of Life Study A021502-HO1 ([Section 14.1](#))
- Biomarker Study A021502-ST1 ([Section 14.2](#))
- Pharmacogenetic Study A021502-PP1 ([Section 14.2](#))

If a patient answers “yes” to “I choose to take part in the Quality of Life study and will fill out these forms,” Question #1 in the model consent, they have consented to participate in the substudy described in [Section 14.1](#). The patient should be registered to Alliance A021502-HO1 at the same time they are registered to the treatment trial (A021502). Questionnaires should be submitted per [Section 6.4](#).

If a patient answers “yes” to “I agree to have my tissue collected, and I agree that my tissue samples and related information may be kept in a Biobank for use in future health research,” “I agree to have my blood collected, and I agree that my blood samples and related information may be kept in a Biobank for use in future health research,” or “I agree to have my stool collected, and I agree that my stool samples and related information may be kept in a Biobank for use in future health research,” questions #2-4 in the model consent, they have consented to participate in the A021502-ST1 substudy described in [Section 14.2](#). If a patient answers “yes” to “I agree to have my blood collected, and I agree that my blood samples and related information may be kept in a Biobank for use in future health research,” Question #2 in the model consent, they have consented to participate in the A021502-PP1 substudy described in [Section 14.2](#). The patient should be registered to Alliance A021502-ST1 and/or A021502-PP1 at the same time they are registered to the treatment trial (A021502). Samples should be submitted per [Section 6.2](#).

#### 4.6 Stratification Factors and Treatment Assignments

##### Permuted Block

After a patient is registered, they will be assigned to one of the two treatment arms (Arm 1 vs. Arm 2) in a **1:1** ratio utilizing a permuted block schedule [39]. The stratification factors for this study are as follows:

- Number of Positive Lymph Nodes: N1 (1-3 positive nodes)/N1C vs. N2 ( $\geq 4$  positive nodes) (per AJCC 7)
- T Stage: Tx/T1-T3 vs. T4
- Primary Tumor Location: proximal (cecum, ascending colon, hepatic flexure, and transverse colon) vs. distal (splenic flexure, descending colon, sigmoid colon, and rectosigmoid junction)

When combined, these stratification factors create eight stratum levels, each of which having its own patient allocation schedule. The possible block size for this study is four.

## 5.0 STUDY CALENDAR

The pre-study testing intervals are guidelines only. Laboratory and clinical parameters during treatment are to be followed using individual institutional guidelines and the best clinical judgment of the responsible physician. It is expected that patients on this study will be cared for by physicians experienced in the treatment and supportive care of patients on this trial.

### Pre-Study Testing Intervals

- To be completed < 28 DAYS before registration: Laboratory studies, history and physical; dMMR testing may be completed at any point prior to registration for the present tumor.
- To be completed ≤ 80 DAYS before registration: Any imaging used to confirm lack of evidence of definitive metastatic disease (pre-surgery scans are acceptable)

	Prior to Registration*	Arm 1: Day 1 of each cycle*	Arm 2: Day 1 of each cycle*	End of treatment follow-up**	Post-treatment follow-up ***
Tests & Observations					
History and Physical, Weight, PS	A	A	A	X	X
Height	X	X(1)	X(1)	X(1)	
Pulse, Blood Pressure	X	X	X	X	
O 2 Saturation	X(2)	X(2)		X(2)	
CTCAE Adverse Event Assessment		X(3)	X(3)	X(3)	X(3)
PRO-CTCAE Adverse Event Assessment	X(4)	X(4)	X(4)	X(4)	
Registration Fatigue/ Uniscale Assessment	X(5)				
Colonoscopy	B				B
Tanner Staging	X(1)	C(1)	C(1)	X(1)	X (1)
Laboratory Studies					
Complete Blood Count, incl. Diff.	X	X	X	X	
Chemistry	X(6)	X(6)	X(6)	X(6)	
TSH	X(7)	X(7)			
Hep B Surface Ag & Hep C ab (Physician Discretion)	X				
Serum or Urine HCG	X(8)				
CEA	X(9)	X(9)	X(9)		X(9)
CD4 Count & Viral Load	X(10)				
dMMR Testing	X				
Staging					
CT of Chest/Abd/Pelvis or MRI of Chest/Abd/Pelvis	D	E	E	E	E
Correlative Studies: For patients who consent to participate					
QOL Assessments	Arm 1: At registration, prior to Cycles 4, 7, and 13, at the end of treatment, and 3 years from registration. Arm 2: At registration, prior to Cycles 4 and 7, at the end of treatment, 12 months from registration, and 3 years from registration. See Sections 6.4, 14.1, and Appendix I .				

Tissue, Blood, and Stool Samples	See Sections 6.2 and 14.2 .
----------------------------------	---

\* Labs and visits completed prior to registration may be used for Day 1 of Cycle 1 (or Day 1 of Cycle 2) tests if obtained  $\leq 14$  days prior to treatment. For subsequent cycles, labs and visits may be obtained  $\leq 2$  business days prior to day of treatment.

\*\* Physical examination, adverse event assessment, labs (CBC and chemistry), and staging scans (if due per footnote D) are required 1 month (+/- 7 days) after the last day of the last treatment cycle.

\*\*\* Patients will be followed for recurrence every 6 months (+/- 1 month) for the first two years after registration, and then once annually (+/- 1 month) for years 3-5 after registration. Recurrence follow-up will continue per the schedule above for 5 years after registration or until evidence of relapse, whichever comes first. See [Section 12.0](#) for survival follow-up.

- 1 For patients aged 12 to <18 years. Staging should be performed until the patient has reached Tanner Stage V.
- 2 Oxygen saturation should be assessed at rest and after 1 minute walk.
- 3 Solicited AEs are to be collected starting prior to treatment until off-treatment (see [Section 9.1](#)). Routine AEs are to be collected starting after registration until the end of survival follow-up. For patients who complete one cycle of FOLFOX prior to registration, the first routine AE assessment should take place after registration but prior to Day 1 Cycle 2 of FOLFOX; see [Section 9.3](#) for expedited SAE reporting.
- 4 Patients aged  $\geq 18$  years complete PRO-CTCAE by paper booklet ordered through the CTSU website. See [Section 9.1](#) for administration instructions. See [Appendix I](#) for PRO-CTCAE assessments for IRB submission and review only. See [Section 4.3](#) for ordering instructions. PRO-CTCAE booklets should be administered at the following time points:  $\leq 14$  days prior to registration; Day 1 of each Cycle, and at the end of treatment.
- 5 To be completed after registration but  $\leq 21$  days prior to treatment. See [Appendix I](#).
- 6 Albumin, alkaline phosphatase, total bilirubin, bicarbonate (or total CO2), BUN, calcium, chloride, serum creatinine, glucose, potassium, total protein, SGOT (AST), SGPT (ALT), and sodium.
- 7 Perform at baseline and then every 8 weeks (+/- 14 days).
- 8 For women of childbearing potential ([Section 3.2.6](#)). Must be done  $\leq 7$  days prior to registration.
- 9 Perform at baseline, 6 weeks (+/- 7 days) after end of FOLFOX, then every 6 months (+/- 1 month) for 3 years, then every 12 months (+/- 1 month) for an additional 2 years, or until relapse. After the end of FOLFOX treatment, the timing of CEA testing should correspond with timing of radiographic imaging studies, where possible, but more frequent testing is at provider discretion.
- 10 HIV-positive patients should complete a CD4 count and viral load  $\leq 28$  days prior to registration.

A Drug dosages need not be changed unless the calculated dose changes by  $\geq 10\%$ , however, if the site recalculates the dose for a lower percentage dose changes (i.e. dose changes that are  $< 10\%$ ) to adhere to institutional policy, then this will not be considered a protocol deviation.

B Patients who did not receive a colonoscopy to the cecum prior to surgery are required to have a full colonoscopy no later than 6 weeks after the completion of chemotherapy, but exact timing within the specified window is per treating physician discretion. If recurrence is observed or suspected on imaging and it has colonic or rectal involvement that is not in close proximity to the surgical anastomosis, then a colonoscopy with biopsy is required to exclude a new primary malignancy in the colorectum. Colonoscopy and pathology reports from all additional colonoscopies performed during the treatment and follow-up periods should be submitted if possible. See [Section 11.3.1](#) for details on follow-up and Lynch Syndrome.

C Perform only on Day 1 of Cycle 1 and Day 1 of Cycle 7.

D Baseline abdominal/pelvic scans can include either: 1) a CT ABD/PELV, or 2) a MRI ABD/PELV. Chest imaging can be either chest CT or chest MRI. CT scans should be of diagnostic quality and performed with oral and IV contrast unless there is a medical contraindication. MRIs should be performed with IV contrast unless there is a medical contraindication. Supporting documentation is to be submitted, per [Section 6.1.1](#).

- E The same imaging modality used at baseline must be used for all subsequent scans. Every 6 months (+/- 1 month) for the first 2 years after registration, and then annually (+/- 3 months) for years 3-5 after registration or until evidence of relapse, whichever comes first. Imaging and reports are to be submitted per Section 6.3. Upon relapse documented by imaging, reports should be submitted for retrospective review by Study Chair per [Section 6.1.1](#).

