**3.2.7 Required Initial Laboratory Values:**

Absolute Neutrophil Count (ANC)	$\geq 1500 \text{ mm}^3$
Platelet Count	$\geq 100,000 \text{ mm}^3$ *
Creatinine	$\leq 1.5 \times$ upper limit of normal (ULN)
or	
Calculated Creatinine Clearance	$\geq 45 \text{ mL/min}$ **
Total Bilirubin	$\leq 1.5 \times$ upper limit of normal (ULN)***
AST / ALT	$\leq 2.5 \times$ upper limit of normal (ULN)
TSH	WNL****

\* Platelets  $\geq 75,000$  required for patients who received Cycle 1 of mFOLFOX6 prior to registration

\*\* By Cockcroft-Gault equation. Alternatively, for patients < 18 years of age, maximum serum creatinine  $\leq$  the below age-sex-specific norms:

Creatinine (mg/dL)		
Age	Male	Female
12 years	1.2	1.2
13 to <16 years	1.5	1.4
16 to <18 years	1.7	1.4

\*\*\* Except in the case of Gilbert disease

\*\*\*\* Supplementation is acceptable to achieve a TSH WNL. In patients with abnormal TSH, if Free T4 is normal and patient is clinically euthyroid, patient is eligible.

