### 3.2.8 Comorbid Conditions

No active known autoimmune disease, including colitis, inflammatory bowel disease (i.e. ulcerative colitis or Crohn's disease), rheumatoid arthritis, panhypopituitarism, adrenal insufficiency.

No known active hepatitis B or C.

- Active Hepatitis B can be defined as:
  - HBsAg detectable for > 6 months;
  - Serum HBV DNA 20,000 IU/ml (105 copies/ml); lower values 2,000-20,000 IU/ml (104-105 copies/ml) are often seen in HBeAg-negative chronic hepatitis B;
  - Persistent or intermittent elevation in ALT/AST levels;
  - Liver biopsy showing chronic hepatitis with moderate or severe necroinflammation.
- Active Hepatitis C can be defined as:
  - Hepatitis C AB positive, AND
  - Presence of HCV RNA

Excluded if known active pulmonary disease with hypoxia defined as:

- Oxygen saturation < 85% on room air, or
- Oxygen saturation < 88% despite supplemental oxygen

No grade  $\geq 2$  peripheral motor or sensory neuropathy.

Patients positive for HIV are eligible only if they meet all of the following:

- A stable regimen of highly active anti-retroviral therapy (HAART)
- No requirement for concurrent antibiotics or antifungal agents for the prevention of opportunistic infections
- A CD4 count above 250 cells/mcL, and an undetectable HIV viral load on standard PCR-based tests

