6. Any manuscripts reporting the results of this clinical trial must be provided to CTEP by the Group office for Cooperative Group studies or by the principal investigator for non-Cooperative Group studies for immediate delivery to Collaborator(s) for advisory review and comment prior to submission for publication. Collaborator(s) will have 30 days from the date of receipt for review. Collaborator shall have the right to request that publication be delayed for up to an additional 30 days in order to ensure that Collaborator's confidential and proprietary data, in addition to Collaborator(s)'s intellectual property rights, are protected. Copies of abstracts must be provided to CTEP for forwarding to Collaborator(s) for courtesy review as soon as possible and preferably at least three (3) days prior to submission, but in any case, prior to presentation at the meeting or publication in the proceedings. Press releases and other media presentations must also be forwarded to CTEP prior to release. Copies of any manuscript, abstract and/or press release/ media presentation should be sent to:

Email: [[contact]](mailto:[contact])

The Regulatory Affairs Branch will then distribute them to Collaborator(s). No publication, manuscript or other form of public disclosure shall contain any of Collaborator's confidential/ proprietary information.

### APPENDIX III STANDARD OF CARE FOLFOX PRIOR TO REGISTRATION CYCLE 1

Patients may receive one cycle of mFOLFOX6 prior to registration to the trial, in the event that they are still in screening or have not yet made a decision to enroll. Treatment must be administered at the institution that intends to register the patient should they meet all eligibility criteria and consent to participate (i.e. the registering institution). The doses received of Cycle 1 of mFOLFOX6 must be the following:

- 5-FU 400 mg/m^2 bolus followed by 2400 mg/m^2 over 2 days
- Leucovorin 400 mg/m^2 \*
- Oxaliplatin 85 mg/m^2

\* Minor variations (<10%) in leucovorin dose for prior to registration Cycle 1 of mFOLFOX6 are permitted if needed to adhere to local institutional policy.

Infusion rates and length of infusion are per institutional standard. Prior to receiving Cycle 2 of mFOLFOX6 on study, the patient must meet all lab parameters as described in eligibility criteria, which must be verified in the OPEN eligibility checklist, in order to be registered and randomized.

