Please note that [Section 8.0](#) should be followed for Cycle 2 onward, based on the experienced toxicity with Cycle 1 and beyond.

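### For patients who had Cycle 1 of mFOLFOX6 before registration, footnote * of Section 5.0 lets blood tests up to 14 days old stand as the Cycle 2 Day 1 tests

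*Combined protocol and SAP*

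**What the plan says.** - **Pre-registration cycle.** Sections 3.2.3 and 7.0 and Appendix III allow one cycle of mFOLFOX6 before registration. Cycle 2 is then the first on-study cycle, and on Arm 1 it is also the first dose of atezolizumab.
- **Screening window.** Section 5.0, Pre-Study Testing Intervals: "To be completed < 28 DAYS before registration: Laboratory studies, history and physical".
- **Reuse as Day 1 tests.** Footnote *, attached to the pre-registration column and to the Day 1 columns of both arms: "Labs and visits completed prior to registration may be used for Day 1 of Cycle 1 (or Day 1 of Cycle 2) tests if obtained" within 14 days before treatment. It continues "For subsequent cycles, labs and visits may be obtained" up to 2 business days before the treatment day.
- **Dose modification.** Section 8.2 bases decisions on toxicity since the last dose, except that blood counts are those of Day 1 of the cycle. Section 8.2.1.1 turns those counts into delays, dose reductions and loss of the 5-FU bolus.
- **Rules written for this subgroup.** Section 3.2.7 sets a platelet limit of 75,000 "required for patients who received Cycle 1 of mFOLFOX6 prior to registration". Appendix III says: "Prior to receiving Cycle 2 of mFOLFOX6 on study, the patient must meet all lab parameters as described in eligibility criteria". It makes this a condition of registration, to be confirmed through OPEN. Its closing note says that Section 8.0 "should be followed for Cycle 2 onward, based on the experienced toxicity with Cycle 1 and beyond".
- **German sites.** AIO appendix Section 3.1.2 puts hematology and chemistry on Day 1 of every 14-day cycle, +/- 2 business days, unless indicated otherwise.

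**The concern.** The Cycle 2 Day 1 blood count is there to show whether the patient has recovered from Cycle 1. A sample taken before the Cycle 1 dose carries no information on that, and one taken early in the cycle may no longer describe the patient on the dosing day. Under footnote * either can be entered as the Cycle 2 Day 1 test.

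What is at stake is a Cycle 2 dose given in full and on time when a current count would have called for a delay or a reduction under Section 8.2.1.1. That is a matter of individual patient safety. It does not bear on the treatment comparison.

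**Working it through.** The plan states no figure here, so the check is day arithmetic and a comparison of the rules.

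**Inputs**
- Section 3.2: the day of a test counts as Day 0. Set Cycle 1 Day 1 as day 0, Cycle 2 on day c, the sample on day d and registration on day r.
- Footnote *: c − d ≤ 14, so d ≥ c − 14, with the sample taken before registration.
- Section 7.0: the standard start-to-start interval is 14 days. Up to 28 days may pass between Day 14 of Cycle 1 (day 13) and Cycle 2, so the latest c is 13 + 28 = 41. A dose may be given one business day early. Treatment starts within 14 days after registration.

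**Earliest sample that footnote * accepts**

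| Cycle 2 on day c | Earliest d = c − 14 | Meaning |
|---|---|---|
| 11 (due Monday, given the preceding Friday) | −3 | 3 days before Cycle 1 |
| 13 (one day early) | −1 | 1 day before Cycle 1 |
| 14 (on schedule) | 0 | Cycle 1 Day 1, pre-dose |
| 15 | 1 | day after the Cycle 1 dose |
| 41 (latest allowed) | 27 | within the prolonged Cycle 1 |

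**Do other limits exclude the day-0 sample when c = 14?** Starting treatment within 14 days after registration gives r ≥ 14 − 14 = 0, so any registration after the Cycle 1 dose and up to day 14 is allowed. The screening window needs r − 0 < 28, which holds for every such r. Neither limit excludes it.

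**Rules side by side for the Cycle 2 count**
- Footnote *: up to 14 days old.
- Section 8.2: the count of Day 1 of the cycle.
- AIO Section 3.1.2: Day 1 +/- 2 business days.

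**Under a limit of 2 business days before Cycle 2** (holidays aside), the oldest sample is 4 calendar days old for a Monday dose (Thursday) or a Tuesday dose (Friday), and 2 days old for Wednesday to Friday. With c = 14 the earliest draw is day 14 − 4 = 10 or 14 − 2 = 12. With c = 11 on a Friday it is day 9. All of these follow Cycle 1.

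**The case against.** **The allowance is deliberate.** Footnote * names Cycle 2 Day 1, so its authors had this patient in mind. A reader might infer that the footnote contradicts itself, with 14 days in one sentence and 2 business days in the next. It does not, because the tighter limit is confined to later cycles. The tension is with Section 8.2.

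**Its reach is short.** A sample taken before the Cycle 1 dose qualifies only when Cycle 2 is on time or early. That stands. From day 15 onward the problem is an old count, and no longer a pre-chemotherapy one.

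**Other rules protect Cycle 2.** Section 8.2 governs dosing, Appendix III applies Section 8.0 to Cycle 1 toxicity, and footnote 3 of Section 5.0 asks for an adverse event assessment between registration and Cycle 2. Section 5.0 also calls the pre-study intervals guidance and leaves on-treatment parameters to institutional practice and clinical judgment. Much of this stands, and many sites will draw a fresh count anyway. But footnote * says what may serve as a Day 1 test, so a site can read Section 8.2 as satisfied by the older sample. The guidance remark concerns pre-study intervals and does not remove the Day 1 allowance.

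**Two stronger readings are tempting.**
- *That the 28-day window lets these patients register on pre-chemotherapy labs.* No sentence dates the eligibility draw after Cycle 1. However, Appendix III requires the lab parameters to be met before Cycle 2 and verified in order to register, and the 75,000 platelet limit makes sense only for a count after Cycle 1. The intent is plain, and only a detail is missing.
- *That neuropathy must be re-graded after Cycle 1.* Section 3.2.8 excludes grade 2 or higher "peripheral motor or sensory neuropathy" as a state of the patient, whatever the date of the last examination. For adults, PRO-CTCAE is due within 14 days before registration and asks about numbness or tingling, which covers part of the gap. Section 10.4 says first-course symptoms usually last less than a week, so compulsory re-grading could cause screen failures over transient symptoms.

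**Conclusion.** The point holds and is minor. Footnote * states a rule under which CBC and chemistry up to 14 days old can stand as Cycle 2 Day 1 tests in patients who had Cycle 1 before registration, including a Cycle 1 Day 1 pre-dose sample when Cycle 2 is on day 14. That is at odds with Section 8.2 and looser than the AIO schedule.

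The rule does not depend on arm, and no power, alpha or DFS figure changes. The documents do not say how many patients use a pre-registration cycle or how often a fresh count would change the Cycle 2 dose, so no number of affected patients is claimed. The conclusion assumes that sites apply footnote * as written. It does not extend to a finding that eligibility is unsafe for these patients or that neuropathy screening is deficient.

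**What to change.** Add one clause to footnote *: for patients who received Cycle 1 of mFOLFOX6 before registration, the CBC and chemistry used for Cycle 2 Day 1 must be drawn after Cycle 1 and no more than 2 business days before Cycle 2. Keep the 14-day allowance for visits made after Cycle 1; a visit on day 8, for example, is 6 days before a day-14 Cycle 2 and stays usable.

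The cost is an occasional repeat blood draw. The study calendar already schedules CBC and chemistry on Day 1 of each cycle, and the AIO schedule already works to a similar limit. A cross-reference from the 28-day bullet to Appendix III would be a useful clarification but is optional.

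The documents do not settle whether accrual is still open. If it is closed, the clause matters only on re-opening, which Section 13.5 contemplates.
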